5. STATISTICAL ANALYSIS

5.1. General Considerations

The analytic plan is designed to determine preliminary efficacy of the intervention by comparing pre/post assessments of employment and sexual risk behaviors. Descriptive statistics will be used to analyze the proportions and central tendencies for participant sociodemographic covariates collected in the surveys. We will first generate frequencies, means, and other measures of central tendency as appropriate to describe our sample and outcomes at each of the three time points (baseline, post-intervention, and 8-month follow-up).

Changes in primary and secondary outcomes between baseline and 8-month follow-up will be assessed using paired t-tests for continuous variables and McNemar's test for matched categorical variables. We will use standard diagnostic tools to assess the appropriateness of the normality assumption (e.g., QQ-plots) and, if approximate normality of the residuals is not tenable, a non-parametric test for continuous paired data, i.e. Wilcoxon sign rank test will be used. All hypothesis testing will be done at an alpha-level of 0.1, given the exploratory nature of the study.

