## 3.0 STUDY DESIGN

[figure not shown]
All research activities except for the community-based pilot will occur at the University of Chicago (UC), Center for Interdisciplinary Inquiry and Innovation in Sexual and Reproductive Health (Ci3). Ci3 is a foundation and federally funded research center focused on advancing adolescent sexual and reproductive health and rights through innovative research methodologies, intervention strategies, and novel solutions to broad social problems. Ci3 has a dedicated research team skilled in cross-disciplinary collaboration focused on adolescent health along with a broad network of community partners working with LGBT adolescents, and environments that will support the successful development, implementation, and evaluation of the project.

Community-based pilot-testing will be conducted by study staff in the community at the following organizations:

- The Village (Chicago Center of HIV Elimination, University of Chicago)
- TaskForce Prevention and Community Services
- Ann & Robert H. Lurie Children's Hospital of Chicago

Each community setting has a private area for the confidential conduct of the study, including study visits and workshop sessions.

**Conceptual Model:** Our conceptual model (Figure 1) draws on the existing iFOUR theoretical framework that operationalizes the Health Belief Model (HBM) and the Supported Employment Model (SE) to hypothesize the potential relationship between adolescent employment and HIV risk. We propose that employment, and subsequent economic connection and stability, serves as a structural-level intervention for adolescent HIV. Based on prior research, we hypothesize that the adapted and tailored iFOUR intervention will facilitate increased job seeking self-efficacy and job readiness [Path A] and ultimately increase employment placement and maintenance [Path B]. Further, we hypothesize that establishing economic stability will decrease engagement in HIV risk behaviors and increase HIV prevention and care [Path C], and decrease involvement with known social determinants of HIV (e.g., sex work, drug abuse) [Path D], that are directly linked to HIV transmission and acquisition [Paths E & F] among YMSM and YTW of color.

**Figure 1.** Conceptual Model

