#### Phase II and III

##### 10.3.1.1 Descriptive statistics

Descriptive statistics will be used to analyze the proportions and central tendencies for participant sociodemographic characteristics collected in the surveys completed by participants in the pilot-tests. We will first generate frequencies, means, and other measures of central tendency as appropriate to describe our sample and outcomes at each of the three time points (T1, T2, T3). Sensitivity analyses will be performed to address extreme outlying variables, including the removal of records with extreme outlying values from analyses.

Changes in primary and secondary outcomes between Baseline (T1) and Follow-Up (T3) will be assessed using paired t-tests for continuous variables and McNemar's test for categorical variables. Other statistical tests that appropriately account for the correlation in the dataset will be considered as needed. All hypothesis testing will be done at an alpha-level of 0.1, given the pilot/exploratory nature of the study.

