1.3. JOB SEEKING SELF-EFFICACY SCALE SCORE

Job seeking self-efficacy is defined as one's perceived ability and confidence to perform job search and application activities. Higher values indicate higher self-efficacy. This scale is measured at Baseline (T1) and the Month 8 Follow-up (T3).

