1.3.2. Job Seeking Self-Efficacy Score at Post-Intervention (T2)

Description: Job Seeking Self-Efficacy score at time point T2 (Post-Intervention) is based on 12 items (13a through 13f and 14a through 14f) from the EVL Questionnaire. Responses are scored on the scale 1/Not at all confident = 1 point to 10/Very Confident = 10 points.

Variable: JOBSEEK_T2_1

Label: Job-Seeking Self Efficacy Score at T2

Type: Numeric; Range = 1 to 10

Algorithm: $\text{JOBSEEK_T2_1} = \text{MEAN} (\text{EVL13a, EVL13b, EVL13c, EVL13d, EVL13e, EVL13f, EVL14a, EVL14b, EVL14c, EVL14d, EVL14e, EVL14f})$

If all responses are missing, then $\text{JOBSEEK_T2_1}=\text{Missing}$. Otherwise, calculate the mean of the non-missing responses.

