5. STATISTICAL ANALYSIS

5.1. General Considerations

The analytic plan is designed to determine preliminary efficacy of the intervention by comparing pre and post assessments of employment and sexual risk behaviors. Descriptive statistics will be used to analyze the proportions and central tendencies for participant sociodemographic covariates collected in the surveys. We will first generate frequencies, means, and other measures of central tendency as appropriate to describe our sample and outcomes at each of the three time points (baseline, post-intervention, and 3-month follow-up).

Changes in primary and secondary outcomes between baseline and 3-month follow-up will be assessed using paired t-tests for continuous variables and McNemar's test for matched categorical variables. We will use standard diagnostic tools to assess the appropriateness of the normality assumption (e.g., QQ-plots) and, if approximate normality of the residuals is not tenable, a non-parametric test for continuous paired data, i.e., Wilcoxon sign rank test will be used. All hypothesis testing will be done at an alpha-level of 0.1, given the exploratory nature of the study.

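### Job-seeking self-efficacy is scored at T1, T2 and T3, but the only change variable and test is T1-T3: add a supportive T1-T2 estimate and keep T2 scores out of T1-T3

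*SAP*

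**What the plan says.** In both SAPs, section 2.1 states that preliminary efficacy is evaluated on outcomes assessed at T1, T2 and T3. Appendix 1.3.1 to 1.3.3 derives a job-seeking self-efficacy score at each visit. For the middle one, Appendix 1.3.2 says: "Job Seeking Self-Efficacy score at time point T2 (Post-Intervention) is based on 12 items". The opening of Appendix 1.3 leaves that visit out; in the Phase 2 SAP it reads: "This scale is measured at Baseline (T1) and the Month 8 Follow-up (T3". The Phase 3 SAP has the same omission, with Month 3.

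The only change variable is JOBSEEK_T1T3_1 (Appendix 1.3.4). The Phase 2 test is in 5.1: "Changes in primary and secondary outcomes between baseline and 8-month follow-up will be assessed using paired t-tests for continuous variables". The Phase 3 test is in its own 5.1: "Changes in primary and secondary outcomes between baseline and 3-month follow-up will be assessed using paired t-tests for continuous variables". Protocol 10.3.1.1 agrees: "Changes in primary and secondary outcomes between Baseline (T1) and Follow-Up (T3) will be assessed using paired t-tests". It adds a general clause: "Other statistical tests that appropriately account for the correlation in the dataset will be considered as needed".

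T2 has two other uses. SAP 5.1 plans summaries of outcomes at all three time points. Appendix 1.3.4 puts the T2 score into the T1-T3 change when the T3 score is missing. SAP 3.1, however, limits the T1-T3 change analyses to participants who completed T3.

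**The concern.** The conceptual model in Protocol 3.0 says the adapted intervention "will facilitate increased job seeking self-efficacy and job readiness [Path A] and ultimately increase employment placement and maintenance [Path B". Self-efficacy is thus the near effect and employment the later one. T2 falls within two weeks of the last workshop. By T3 a participant may have found or lost a job, which could itself change job-seeking confidence. The design has no comparison group, and the regression models in SAP 5.4 adjust only for baseline employment.

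If only T1-T3 is tested, a flat result leaves open whether confidence never moved or rose and fell back. That matters because Protocol 2.4 says the study leads to a manual for a large multi-site trial, and the two explanations point to different revisions of that manual. The data needed to inform this are already collected.

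**Working it through.** **Inputs**
- Phase 2 SAP 2.3: up to 70 enrolled, at least 50 completing, about 70% retention. Check: 50/70 = 71.4% and 0.70 × 70 = 49, which agrees. No power calculation was done, so there is none to reproduce.
- Phase 3 SAP 2.3: up to 40 enrolled, no retention figure. Assumed range 28 to 40 (70% to 100%).
- Protocol 8.2: workshops within 12 weeks of baseline (Phase 3: 4). T2 within 2 weeks of the last session, or within 14 weeks (6) of baseline for partial attenders. T3 at 8 months ± 4 weeks (3 months ± 2 weeks) after the last session.
- Alpha, SAP 5.1: "All hypothesis testing will be done at an alpha-level of 0.1, given the exploratory nature of the study". Sidedness is not stated; two-sided is assumed.
- No SD or effect size is given. dz, the mean change divided by the SD of the change, is therefore assumed. The completer count of 50 stands in for the number of T1-T2 pairs.

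**1. Longest intervals from baseline** (one month = 365.25/12/7 = 4.35 weeks)
- Phase 2: T1-T2 is 12 + 2 = 14 weeks; T1-T3 is 12 + 34.8 + 4 = 50.8 weeks; ratio 3.6.
- Phase 3: T1-T2 is 4 + 2 = 6 weeks; T1-T3 is 4 + 13.0 + 2 = 19.0 weeks; ratio 3.2.

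**2. What each test can show.** Power of a paired t-test comes from the noncentral t with n − 1 degrees of freedom and noncentrality dz × √n, at alpha 0.10.
- T1-T3, n = 50, early effect fully faded (dz 0 at T3): non-significant 90% of the time.
- T1-T3, n = 50, no effect at any visit: also 90%.
- T1-T2, n = 50, dz 0.5: noncentrality 0.5 × √50 = 3.54, power 0.97. At dz 0.3, power is 0.67.
- T1-T2 in Phase 3, dz 0.5: power 0.93 (n = 40) or 0.83 (n = 28).

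**3. Precision of a T1-T2 estimate.** The 90% CI half-width is t(0.95, n − 1)/√n in SDs of the change: 0.24 (n = 50), 0.27 (n = 40) and 0.32 (n = 28).

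**4. Effect of the T2 substitution.** Take a true T3 change of 0, a T2 change of dz 0.5, and 50 observed T3 scores plus m substituted T2 scores. The mean of the variable labelled T1-T3 is 0.5m/(50 + m). The rejection rate, nominally 0.10, comes from 20,000 simulated trials.
- m = 5: mean 0.05 SD, rejection 0.11.
- m = 10: mean 0.08 SD, rejection 0.16.
- m = 20: mean 0.14 SD, rejection 0.31.

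The last case corresponds to 50 of 70 completing and all 20 others having a T2 score. If SAP 3.1 governs instead, substitution can reach only participants who attended T3 with no usable self-efficacy item, and the effect is close to nil.

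**The case against.** The T1-T3 change is a legitimate endpoint. It targets lasting change and is defined consistently in the protocol and both SAPs. The stated primary objective is feasibility and acceptability, and the testing is openly exploratory. All of that stands.

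Three stronger readings are tempting, and the documents do not support them.

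- **That the plan is blind to a faded effect, or uses T2 only as a substitute.** SAP 5.1 plans summaries at all three visits, so a rise at T2 that is gone by T3 could be seen in the means. What is missing is a paired change and an interval. Under Protocol 8.2 a participant can miss T2 and still attend T3, so the visit means may also come from different people. The protocol's allowance for other tests names no contrast.
- **That T2 isolates Path A.** Eligibility admits part-time workers (Protocol 4.1.4 and 4.1.5), T2 can fall 14 weeks after baseline in Phase 2, and employment variables are collected at T2. Jobs can be held, gained or lost before then.
- **That T1-T2 is the least confounded estimate.** It is less exposed to elapsed time, but it has biases of its own. The score is self-reported within two weeks of the workshops on the same form as the satisfaction items, and Protocol 8.2 gives no T2 visit to participants who attended no session.

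**Conclusion.** The point holds as a cheap improvement. Neither SAP pre-specifies a T1-T2 change in job-seeking self-efficacy, although the score exists in both phases. The planned test by itself cannot tell no effect from an early effect that faded. The descriptive plan only partly closes that gap.

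The interval ratios (3.6 and 3.2 at the longest permitted timings) follow from the documents. They cannot be converted into scale points, because no rate of background change is given. The power and substitution figures rest on assumed dz values, two-sided tests, 50 pairs in Phase 2 and 28 to 40 in Phase 3.

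A reader might infer that a positive T1-T2 result would show the workshops worked. It would not: with one arm, it shows an immediate change among attenders and nothing firmer. The substitution rule matters as much as the missing contrast. If Appendix 1.3.4 governs, an early effect can appear as a follow-up effect; if 3.1 governs, it hardly can. The SAPs do not say which applies.

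**What to change.** In both SAPs:

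1. In Appendix 1.3, add JOBSEEK_T1T2_1 = JOBSEEK_T2_1 − JOBSEEK_T1_1 for participants with both scores. Analyse it as in 5.1, give a 90% CI, and report it beside T1-T3 as a supportive estimate of immediate change among workshop attenders.
2. Where T1-T3 is read as persistence, compute it from observed T3 scores only, without T2 substitution. Reconcile Appendix 1.3.4 with the T3-completer population in 3.1.
3. Correct the opening of Appendix 1.3 so that T2 is listed as a measurement time.

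No new data are needed. The cost is one derived variable and one more unadjusted p-value per phase. Two tests at 0.10 give a chance of at least one false positive of 1 − 0.9² = 0.19 if they were independent, which is why the new result should be labelled supportive.

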5.2. Missing Data

Missing responses to survey questions will be ignored and non-missing data will be used to compute the primary and secondary outcomes. If all components for an outcome are missing, then the outcome will be considered missing. For those outcomes with unique missing data rules, the handling of missing data for each individual outcome are described in the appendix. Missing data patterns will be explored prior to the analysis of the primary and secondary outcomes.

5.3. Subject Disposition Analyses

Number of participants pre-screened, screened, eligible, discontinued, and included in the Per Protocol analysis population will be reported. In addition, the number of participants completing each visit (T1, T2 and T3) and the reasons for patient discontinuation will be tabulated.

5.4. Analysis of Primary Outcomes

Primary outcomes for analyses include Information Systems Success Model score, workshop completion, change in Job-Seeking Self Efficacy Scale score, Protean Career Attitudes Scale score, change in Self-Directed Attitudes Scale score, and change in Values-Driven Attitudes Scale score. Details about these outcomes are described in Section 4.1.

Univariate analyses will be performed as described in Section 5.1. To the extent that data allows, multivariable analyses will adjust for sociodemographic characteristics, workshop attendance, baseline employment status, and study completeness. Analytical models will include linear regression or generalized linear models for continuous outcomes and logistic regression for binary and categorical outcomes.

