## 2.4 Study Hypotheses/Research Questions

We hypothesize that this intervention will be both feasible and acceptable to the target populations and that the intervention will increase job self-efficacy and readiness, as well as decrease HIV risk behavior. This study will lead to a final intervention manual to be tested in an R01-type, large multi-site trial across the ATN study sites.

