1.1. Objectives and Research Hypotheses

The primary objective of Phase 2 is to pilot-test the intervention among up to 70 at-risk YMSM and YTW of color in order to evaluate feasibility and acceptability. Investigators hypothesize the intervention will increase job self-efficacy and readiness, as well as decrease HIV risk behaviors and STI and HIV infections.

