4.1. Primary Outcomes

4.1.1. Information Systems Success Model Score (T2)

The Information Systems Success Model (ISSM) will be used to assess for intervention acceptability and satisfaction. The 21-item scale measures four sub-domains: information quality, handbook quality, perceived usefulness, and overall satisfaction. Every item is scored on a 1 to 5 scale, with 1 being “Strongly Disagree” and 5 being “Strongly Agree”. Responses are averaged within each sub-domain to produce four sub-domain scores. The four sub-domain scores are then averaged to produce an overall ISSM score (range: 1 to 5; higher scores indicate higher acceptability/satisfaction). This scale has been adapted from Horvath et al.¹

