4.1.2. Workshop Completion (T2)

Workshop completion will be used to assess for intervention feasibility. The outcome of intervention completion will be defined as having attended at least two of the four workshop sessions and will be measured by tracking participant attendance. Workshop completion may also be defined as the number of workshop sessions attended for use in exploratory analyses.

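### The two T2 outcomes that carry each phase's primary objective, ISSM score and workshop completion, get only a descriptive summary: neither SAP gives an interval or a target to read them against.

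*SAP*

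**What the plan says.** - **Objective.** Phase 2 SAP 1.1 states the primary objective as to "pilot-test the intervention among up to 70 at-risk YMSM and YTW of color in order to evaluate feasibility and acceptability". Phase 3 SAP 1.1 says the same for up to 40 participants.
- **Hypothesis.** Protocol 2.4 reads: "We hypothesize that this intervention will be both feasible and acceptable to the target populations". The hypotheses in SAP 1.1 cover only self-efficacy and readiness, risk behaviors, and infections.
- **Acceptability.** SAP 4.1.1: "The Information Systems Success Model (ISSM) will be used to assess for intervention acceptability and satisfaction". The score runs from 1 to 5 and is taken at T2.
- **Feasibility.** SAP 4.1.2: "Workshop completion will be used to assess for intervention feasibility". A participant is a completer after "having attended at least two of the four workshop sessions". This is also a T2 outcome.
- **Analysis.** SAP 5.4 lists both as primary and then says "Univariate analyses will be performed as described in Section 5.1". Section 5.1 first promises descriptive summaries at each of the three time points. It then says: "Changes in primary and secondary outcomes between baseline and 8-month follow-up will be assessed using paired t-tests for continuous variables", with McNemar's test for categorical variables and the Wilcoxon signed rank test as fallback, all at alpha 0.1. Phase 3 has the same text with a 3-month follow-up.
- **Analysis set.** Section 3.1 of both SAPs restricts the workshop evaluation and completion analyses to participants who completed at least one workshop.

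**The concern.** The plan attaches formal tests to the T1-T3 changes, for which it says no power calculation was done. For the two outcomes that answer the stated primary question it offers a point estimate and nothing to read it against. The two-of-four rule classifies one participant; it does not say what share of completers would make the program feasible. Likewise, nothing says what ISSM mean would make it acceptable.

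The answer has a use: Protocol 2.4 expects the work to lead to an intervention manual for a large multi-site trial. Without an interval the reader cannot see how uncertain the estimate is. Without a target fixed in advance, the judgement will be made after the numbers are known.

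**Working it through.** **1. The only numeric aim nearby.** Phase 2 SAP 2.3 aims for at least 50 of 70 completing the study, about 70%. It reproduces: 50/70 = 71.4%, and 0.70 × 70 = 49. It concerns study completion, not workshop completion or ISSM. It has no stated consequence, and Phase 3 SAP 2.3 has no counterpart.

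**2. What each analysis provision does for the two outcomes.**

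| Provision | Effect on ISSM and completion |
|---|---|
| 5.1 descriptive summaries | Apply: a mean and a proportion at T2 |
| 5.1 paired t, Wilcoxon, McNemar | Limited to T1-T3 change; these outcomes have no T1 or T3 value, so 0 pairs |
| 5.4 linear and logistic models | Estimate covariate effects; do not compare a level with a standard |
| Interval, target or decision rule | None in either SAP |

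In the logistic model, adjusting completion for workshop attendance is also circular: Appendix 1.2.2 computes completion from the attendance count.

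**3. Precision of the completion proportion.** Exact (Clopper-Pearson) 90% limits for x of n: lower = Beta quantile 0.05 with parameters (x, n−x+1); upper = Beta quantile 0.95 with parameters (x+1, n−x). The n are the enrolment ceilings, 70 and 40.

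| x/n | Proportion | 90% CI |
|---|---|---|
| 35/70 | 50% | 39.6% to 60.4% |
| 49/70 | 70% | 59.7% to 78.9% |
| 63/70 | 90% | 82.0% to 95.2% |
| 28/40 | 70% | 56.0% to 81.7% |

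**4. What a target would require (illustration only).** Assume a floor of 50% that the lower limit must exceed.
- n = 70: 42 completers give a lower limit of 49.5%, 43 give 50.9%. Minimum 43 (61%).
- n = 40: 25 give 48.3%, 26 give 50.8%. Minimum 26 (65%).

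Requiring the lower limit of a two-sided 90% interval to clear a floor is a one-sided 0.05 rule. At one-sided 0.1 the minimum counts are 41/70 and 25/40. The SAPs do not state whether alpha 0.1 is one- or two-sided.

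**5. Precision of the ISSM mean.** Half-width = t(0.95, n−1) × SD / √n. The documents give neither the SD nor the number of T2 respondents, so SD 0.6 to 1.0, n = 50 (borrowing the Phase 2 completion aim) and n = 28 (70% of 40) are all assumptions.
- n = 50: 1.677 × 0.6 / 7.071 = 0.14; with SD 1.0, 0.24.
- n = 28: 1.703 × 0.6 / 5.292 = 0.19; with SD 1.0, 0.32.

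**6. Effect of the denominator.** Assume 14 of 70 attend no workshop and 42 complete. Completion is 42/70 = 60.0% of those enrolled, but 42/56 = 75.0% in the Section 3.1 population. If 21 attend none and 49 complete, it is 70.0% against 49/49 = 100%. A target therefore means little until its denominator is fixed.

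**The case against.** The strongest reply is that description is the intended plan and is coherent. Section 5.1 limits the paired tests to changes, which these outcomes are not, and its descriptive part covers T2. Protocol 10.3.1 separates assessing feasibility and acceptability from determining preliminary efficacy by pre/post comparison. Protocol 10.3 also calls for descriptive statistics on feasibility, acceptability and satisfaction measures, although that sentence sits under Phase I. The SAP states feasibility and acceptability as an objective, "in order to evaluate feasibility and acceptability", not as a hypothesis, and the Protocol ranks the pilot test as a tertiary objective of the whole project. An exploratory, unpowered pilot need not test feasibility formally.

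Most of this stands. A reader might infer that the SAP prescribes paired tests for outcomes measured once, or that it omits a test it had promised. The documents support neither reading. What the reply does not supply is an interval or a reference value, and a descriptive analysis of a primary objective can carry both.

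A further objection is that any particular floor is a reviewer's preference. That is correct: neither 50% completion nor the scale midpoint of 3 for ISSM has a basis in the documents. With n = 50 and an assumed SD of 0.8, the half-width is 0.19, so an ISSM mean of about 3.2 would clear a floor of 3. The targets are for the sponsor to set.

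**Conclusion.** The point holds as a gap in reporting and interpretation in both SAPs. The feasibility and acceptability outcomes will be summarised, but without an interval or a pre-stated target, so no completion rate and no ISSM mean could count against the primary objective. It does not hold as a claim that Section 5.1 is misapplied, or that a promised hypothesis test is missing.

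The uncertainty left unreported is material: roughly 10 percentage points either side of a 70% completion rate at n = 70, and roughly 13 at n = 40. These figures assume full enrolment. The ISSM half-widths rest on the assumed SD and respondent numbers, and the 50% floor is an illustration. Correcting this is a cheap improvement that should be made; it is not an error that invalidates the plan.

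**What to change.** In 5.4 of both SAPs, replace the pointer to 5.1 for these two outcomes with text to this effect:

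- Workshop completion is reported as a proportion of all enrolled participants with an exact two-sided 90% CI.
- Mean ISSM is reported among T2 respondents, with their number and a t-based 90% CI.
- Each is read against a target that the sponsor sets and justifies before any T2 data are summarised. The text says whether the target applies to the estimate or to the lower limit. If to the lower limit, it notes that this is a one-sided 0.05 rule.

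Amend 3.1 of both SAPs so that the completion analysis includes enrolled participants who attended no workshop. Appendix 1.2.1 already allows a count of 0, but it sets attendance to missing when every attendance item is blank, so also state how such participants are counted.

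The cost is SAP wording, with no new data collection. The downsides are that the pilot can miss its own criterion, and that the completion figure will be lower than among attenders only whenever some enrolled participants attend no workshop.
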